9.2 AEs, SAEs and SUSARs

9.2.1 Adverse events (AEs)

Adverse events are defined as any undesirable experience occurring to a subject during the study, whether or not considered related to [the investigational product / trial procedure/ the experimental intervention]. All adverse events reported spontaneously by the subject or observed by the investigator or his staff will be recorded.

9.2.2 Serious adverse events (SAEs)

A serious adverse event is any untoward medical occurrence or effect that

- results in death;
- is life threatening (at the time of the event);
- requires hospitalisation or prolongation of existing inpatients' hospitalisation;
- results in persistent or significant disability or incapacity;
- is a congenital anomaly or birth defect; or
- any other important medical event that did not result in any of the outcomes listed above due to medical or surgical intervention but could have been based upon appropriate judgement by the investigator.

An elective hospital admission will not be considered as a serious adverse event.

< Please describe the procedures for handling the serious adverse events. If certain SAEs do not require immediate reporting by the investigator to the sponsor, please specify.>

The investigator will report all SAEs to the sponsor without undue delay after obtaining knowledge of the events, except for the following SAEs: *<specify which*

SAEs do not require immediate reporting by the investigator to the sponsor, if applicable>

The sponsor will report the SAEs through the web portal *ToetsingOnline* to the accredited METC that approved the protocol, within 7 days of first knowledge for SAEs that result in death or are life threatening followed by a period of maximum of 8 days to complete the initial preliminary report. All other SAEs will be reported within a period of maximum 15 days after the sponsor has first knowledge of the serious adverse events.

< If certain SAEs do not require(expedited) reporting to the accredited METC, please specify these SAEs as well as the frequency of reporting of these SAEs in line listings, or in a annual safety report or otherwise.>

9.2.3 Suspected unexpected serious adverse reactions (SUSARs)

<This chapter is only applicable for studies with an investigational medicinal product>

Adverse reactions are all untoward and unintended responses to an investigational product related to any dose administered.

Unexpected adverse reactions are SUSARs if the following three conditions are met:

1. the event must be serious (see chapter 9.2.2);
2. there must be a certain degree of probability that the event is a harmful and an undesirable reaction to the medicinal product under investigation, regardless of the administered dose;
3. the adverse reaction must be unexpected, that is to say, the nature and severity of the adverse reaction are not in agreement with the product information as recorded in:
 - Summary of Product Characteristics (SPC) for an authorised medicinal product;
 - Investigator's Brochure for an unauthorised medicinal product.

The sponsor will report expedited the following SUSARs through the web portal *ToetsingOnline* to the METC *<reporting via webportalToetsingOnline is only applicable for investigator initiated studies>*:

- SUSARs that have arisen in the clinical trial that was assessed by the METC;

- SUSARs that have arisen in other clinical trials of the same sponsor and with the same medicinal product, and that could have consequences for the safety of the subjects involved in the clinical trial that was assessed by the METC.

The remaining SUSARs are recorded in an overview list (line-listing) that will be submitted once every half year to the METC. This line-listing provides an overview of all SUSARs from the study medicine, accompanied by a brief report highlighting the main points of concern.

The expedited reporting of SUSARs through the web portal Eudravigilance or ToetsingOnline is sufficient as notification to the competent authority.

The sponsor will report expedited all SUSARs to the competent authorities in other Member States, according to the requirements of the Member States.

The expedited reporting will occur not later than 15 days after the sponsor has first knowledge of the adverse reactions. For fatal or life threatening cases the term will be maximal 7 days for a preliminary report with another 8 days for completion of the report.

< For multicentre studies the responsibilities of investigators in participating centres as well as of the coordinating investigator should be clearly defined >

<Please describe also the method of breaking the code for SUSAR reporting.>

9.3 Annual safety report

<This chapter is only applicable for studies with an investigational medicinal product>

< The annual safety report may be combined with the annual progress report (see chapter 12.4).>

In addition to the expedited reporting of SUSARs, the sponsor will submit, once a year throughout the clinical trial, a safety report to the accredited METC, competent authority, and competent authorities of the concerned Member States.

This safety report consists of:

- a list of all suspected (unexpected or expected) serious adverse reactions, along with an aggregated summary table of all reported serious adverse reactions, ordered by organ system, per study;

- a report concerning the safety of the subjects, consisting of a complete safety analysis and an evaluation of the balance between the efficacy and the harmfulness of the medicine under investigation.

9.4 Follow-up of adverse events

All AEs will be followed until they have abated, or until a stable situation has been reached. Depending on the event, follow up may require additional tests or medical procedures as indicated, and/or referral to the general physician or a medical specialist. SAEs need to be reported till end of study within the Netherlands, as defined in the protocol

9.5 [Data Safety Monitoring Board (DSMB) / Safety Committee]

<In case a DSMB is established to perform ongoing safety surveillance and to perform interim analyses on the safety data, this committee should be an independent committee. The composition of the DSMB should be described and it should be clear that each member has no conflict of interest with the sponsor of the study. The task and responsibility of the DSMB should be described (see chapter 10.4 for interim analyses either for safety or for futility or positive efficacy) >

<Criteria on which the DSMB may decide to terminate the trial prematurely should be clearly defined before the trial has started.>

The advice(s) of the DSMB will only be sent to the sponsor of the study. Should the sponsor decide not to fully implement the advice of the DSMB, the sponsor will send the advice to the reviewing METC, including a note to substantiate why (part of) the advice of the DSMB will not be followed.

< In case a DSMB is not needed, but some safety review is deemed appropriate, information on this safety committee should be given here. Information should be provided on the composition of the committee and (in)dependence of the members, the reason to establish this committee, type of data that will be reviewed and moment of review, possible measures to be taken>

10. STATISTICAL ANALYSIS

Patient survival, death-censored graft survival and eGFR will be reported as mean \pm standard deviation (SD) if normally distributed or median with interquartile range (IQR) if data is skewed. Categorical variables such as the incidence rate of vascular complications will be described as numbers and percentages. Continuous variables will be compared using student's t-test or Mann–Whitney U test. Categorical variables will be compared using χ^2 test or Fisher's exact test. Kaplan-Meier curves and log-rank test will be used to compare patient and graft survival. The data will be analyzed in SPSS. A p-value of < 0.05 is considered statistically significant.

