1. INTRODUCTION AND RATIONALE

Kidney transplantation has been recognized as the paramount therapy for end stage renal disease. It increases the quality of life and survival rate of patients when compared with long-term hemodialysis(1). For patients who are ineligible for kidney transplantation, peritoneal dialysis or hemodialysis is the only alternative option. According to the annual data report of 2016 from the United States Renal Data System, the overall 5 year survival of hemodialysis patients is 41,6% and for peritoneal dialysis 59,4% (2). In comparison to those survival rates, the survival rate in patients receiving a deceased-donor kidney transplant was 75,7% and for patients receiving a living-donor kidney transplant 84,6%(2). Therefore, kidney transplantation should be the first choice of therapy in patients with end stage renal disease. There is little known about the proportion of renal transplant candidates who are considered ineligible by the transplant center. Kianda et al. investigated that 8% of the referred patients were considered ineligible and he described in 44% of the patients aorto-iliac atherosclerosis as the only reason (3). Other less frequent reasons for ineligibility in this study were severe ischemic heart disease, advanced age, metastatic neoplasia and severe impairment of general status or a combination of these factors. This shows that aorto-iliac atherosclerosis is the most frequent reason why patients are considered ineligible for kidney transplantation.

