3. STUDY DESIGN

This single-center retrospective study includes all kidney transplant patients who underwent kidney transplantation in Erasmus MC between 2010 and 2020. Data of patient characteristics, operation details and long-term outcomes will be collected. All patients will be divided into non-stenosis group and stenosis group based on the existence of pre-transplant aortoiliac stenosis. Propensity score matching will be used to make the baseline characteristics comparable between two groups. Patient survival, graft survival and long-term renal function of the two groups will be compared to indicate if the aortoiliac stenosis has an impact on the survival of transplant patients.

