4.2 Inclusion criteria

Patients who underwent kidney transplantation in Erasmus MC between Jan 2010 and December 2020 will be included in the study.

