10.1 Primary study parameter(s)

Patient survival is defined as the time from transplantation to death or the last follow-up. Death-censored graft survival is defined as the time from transplantation to graft failure or the last follow-up with a functioning graft, with censoring death with a functioning graft.

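### Both primary survival endpoints are to be summarised as mean ± SD or median (IQR) although the times are censored, so the figures would be too low and would move with the data cut-off

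*Combined protocol and SAP*

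**What the plan says.** Section 10 puts the two primary endpoints and eGFR under one reporting rule: "Patient survival, death-censored graft survival and eGFR will be reported as mean" ± SD "if normally distributed or median with interquartile range (IQR) if data is skewed". The rule depends only on the shape of the distribution and does not mention censoring.

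Section 10.1 defines the endpoints as follows:
- **Patient survival:** "Patient survival is defined as the time from transplantation to death or the last follow-up".
- **Death-censored graft survival:** "time from transplantation to graft failure or the last follow-up with a functioning graft, with censoring death with a functioning graft".

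For comparing the groups, Section 10 says "Kaplan-Meier curves and log-rank test will be used to compare patient and graft survival". It also sends continuous variables in general to a t-test or Mann-Whitney test, without excluding survival times.

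Entry is staggered over 11 calendar years (Section 4.2: "Patients who underwent kidney transplantation in Erasmus MC between Jan 2010 and December 2020 will be included in the study"). No data cut-off or minimum follow-up is given, and survival probabilities at fixed times are not planned.

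**The concern.** By the plan's own definitions both endpoints are right-censored. An ordinary mean or median of the recorded times counts a patient alive at last contact as if survival had ended that day. It likewise counts a graft still working at death or last contact as if it had failed. Three things follow.

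- The summary figures for both primary endpoints would be too low in each group, and a later cut-off would raise them even with mortality unchanged.
- The report would contradict itself. At the background survival rate, a median survival of about 5 years would stand beside a Kaplan-Meier curve showing about three quarters of patients alive at that time.
- If follow-up differed between the stenosis and non-stenosis groups, their means and medians would differ even with identical survival.

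The stated aim is to describe short and long term outcomes, so readers would take these figures as prognosis.

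**Working it through.** **The plan's own figure.** The plan gives no survival summary to reproduce. Its one related calculation is the sample size in Section 4.4, made for a t-test. With d = 0.5 and 105 per group, δ = 0.5 × √(105/2) = 3.6228, df = 208, critical t = 1.9714 and power = 0.9501, as stated. It matters here only because it shows that a t-test was in mind.

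**Direction.** The recorded time is X = min(T, C), where T is the true event time and C the available follow-up. X never exceeds T, so the mean and median of X cannot exceed those of T, whatever the survival pattern. A later cut-off lengthens every C and so raises both.

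**Inputs for the size.**
- Survival of 75.7% (deceased donor) and 84.6% (living donor), from Section 1. They are set there against five-year dialysis figures and are taken as five-year values, S5. They are background registry figures, not data from this cohort.
- A higher-mortality case, S5 = 60%: an assumption.
- Entry uniform over 2010-2020 (window from Section 4.2; uniformity assumed).
- Cut-off at end 2020, 2021 or 2023 (assumed), so C is uniform on 0-11, 1-12 or 3-14 years.
- T exponential with rate λ = -ln(S5)/5, and no other loss to follow-up (assumed).

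**Formulas.** With C uniform on (a, b):
- censored share = (e^(-λa) - e^(-λb)) / (λ(b - a))
- raw mean = (1 - censored share)/λ
- raw median: the t at which P(T > t) × P(C > t) = 0.5
- restricted mean to h = (1 - e^(-λh))/λ

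**Worked case, S5 = 75.7%, cut-off end 2020.** λ = -ln(0.757)/5 = 0.05568 and 1/λ = 17.96. The censored share is (1 - 0.542)/(0.05568 × 11) = 0.748. The raw mean is (1 - 0.748) × 17.96 = 4.53 years. The restricted mean to 11 years is (1 - 0.542) × 17.96 = 8.23 years.

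| S5 | Cut-off (end of) | Censored | Raw mean (years) | Raw median (years) | Truly alive at raw median |
|---|---|---|---|---|---|
| 75.7% | 2020 | 74.8% | 4.53 | 4.09 | 79.6% |
| 75.7% | 2021 | 70.7% | 5.26 | 4.81 | 76.5% |
| 75.7% | 2023 | 63.3% | 6.60 | 6.22 | 70.7% |
| 84.6% | 2020 | 83.7% | 4.88 | 4.59 | 85.8% |
| 84.6% | 2023 | 75.7% | 7.27 | 7.04 | 79.0% |
| 60% | 2020 | 60.1% | 3.91 | 3.30 | 71.4% |
| 60% | 2023 | 44.2% | 5.46 | 4.91 | 60.5% |

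**Reading the table.**
- At 75.7% the SD is 3.07 to 3.59 years. The restricted mean over the same maximum follow-up (11, 12, 14 years) is 8.23, 8.75 and 9.72 years.
- The cut-off alone moves the raw mean by 6.60/4.53 = 1.46, a rise of 46%.
- At 60% the true median is ln 2/λ = 6.78 years. It lies within the observable follow-up, yet the raw median is 3.3 to 4.9.

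**Two limiting cases.**
- If no patient died, the raw mean would be the mean of C: 5.5, 6.5 or 8.5 years.
- The documents give no graft-failure rate, but an upper bound exists. If no graft ever failed, Kaplan-Meier graft survival would be 100%. The raw mean would still be only 4.53 to 6.60 years at 75.7% patient survival, because times end at death or last follow-up.

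**Group illustration (assumed).** Take S5 = 75.7% in both groups and a cut-off at end 2021. If one group entered over 2012-2020, C is uniform on 1-10: raw mean 4.60 and median 4.29. The other group, entering over 2010-2020, has 5.26 and 4.81. Survival is identical.

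**The case against.** The strongest reply is that the plan does not say censoring will be ignored. The same paragraph assigns Kaplan-Meier methods to both endpoints, and Section 10.1 names censoring for the graft, so median with IQR might mean Kaplan-Meier quartiles. That reading does not fit the text. The choice between summaries turns on normality or skewness, eGFR falls under the same rule, and mean ± SD has no such interpretation. Nor would the Kaplan-Meier median always exist: under the 84.6% scenario, 62.6% are still alive at the maximum follow-up of 14 years.

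A second reply is that the study question is whether the groups differ, and the log-rank test answers that while handling censoring. This stands, and it limits the point to the descriptive figures. It does not settle how the log-rank test should allow for the matching planned in Section 3, which is a separate matter. The general t-test sentence and the t-test sample size also leave open a comparison of survival times as ordinary continuous variables, so the plan should exclude it.

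A third reply is that the size rests on assumptions and that nothing in the documents shows follow-up differing by group. That is correct. The group example shows only what could happen, and the background rates may not fit this cohort. The direction of the bias depends on none of this.

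**Conclusion.** The concern holds. Followed as written, Section 10 gives summary figures for both primary endpoints that are too low and that depend on the cut-off. At 75.7% five-year survival the raw mean is about 55% to 68% of the restricted mean over the same follow-up (4.53/8.23 and 6.60/9.72). The size rests on exponential survival, uniform entry, no other loss to follow-up, assumed cut-offs and background survival rates; the downward direction does not. The defect is one of descriptive reporting and leaves the planned log-rank result unaffected. It should be fixed because it concerns both primary endpoints and the correction costs almost nothing.

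**What to change.** In Section 10, take patient survival and death-censored graft survival out of the mean ± SD / median (IQR) sentence and leave eGFR there. Then add wording such as:

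> Patient survival and death-censored graft survival will be reported per group as Kaplan-Meier estimates with 95% CI at fixed times (e.g. 1, 5 and 10 years), and as Kaplan-Meier medians if reached. Length of follow-up will be described separately per group. The t-test and Mann-Whitney test do not apply to these two endpoints.

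The particular time points are for the investigators to choose. The planned log-rank test stays, and the wording leaves room for a Cox model or a test that accounts for the matching. The cost is two or three sentences, with no new data and no change to the planned Kaplan-Meier and log-rank comparison.

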10.1 Primary study parameter(s)

Patient survival is defined as the time from transplantation to death or the last follow-up. Death-censored graft survival is defined as the time from transplantation to graft failure or the last follow-up with a functioning graft, with censoring death with a functioning graft.

10.2 Secondary study parameter(s)

Data of eGFR will be extracted from Clinical Chemistry department of Erasmus MC. Vascular complications are defined as the occurrence of steal syndrome, renal artery haemorrhage and thrombosis.

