4. STUDY POPULATION

4.1 Population (base)

The research population are patients (n= ~2000) who underwent kidney transplantation in Erasmus MC between Jan 2010 and December 2020. Based on the pre-transplant existence of aortoiliac stenosis, all patients will be divided into non-stenosis group (n=~1800) and stenosis group (n=~120).

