8.1.2 Secondary study parameters/endpoints (if applicable)

Secondary outcome measures are renal function (such as eGFR) and vascular complications.

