11.2 Recruitment and consent

Gathering the express consent of test subjects is only possible by exerting disproportionate effort or would lead to unacceptable selection bias. All allogeneic kidney transplantation recipients from 2010 to 2020 are included in this study. The study population concerns patients that have been treated 10 years ago; A substantial amount of the study population is expected to have passed away and/or has no records available about current whereabouts. Asking express consent could result in an unacceptable selection bias and therefore produce unreliable data. Recovering addresses would involve a disproportionate effort for gathering the express consent of test subjects. The Form exception informed consent is attached as a separate document.

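### Reported eGFR from the centre's laboratory, with no single equation and no count of who has a value, can distort the secondary renal comparison if calendar time or completeness differs between groups

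*Combined protocol and SAP*

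**What the plan says.** Section 8.1.2 sets the endpoint: "Secondary outcome measures are renal function (such as eGFR) and vascular complications". Section 3 promises a between-group result: "Patient survival, graft survival and long-term renal function of the two groups will be compared". The source is given in section 10.2: "Data of eGFR will be extracted from Clinical Chemistry department of Erasmus MC". Section 8.3 adds no tests, so a value exists only where a sample was taken in routine care.

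The cohort is patients "who underwent kidney transplantation in Erasmus MC between Jan 2010 and December 2020". For the analysis, section 10 says "Continuous variables will be compared using student's t-test", with Mann–Whitney as the alternative. For confounding, section 3 says "Propensity score matching will be used to make the baseline characteristics comparable between two groups".

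The document does not give:
- an eGFR equation, or whether eGFR is recalculated from creatinine;
- a time point or window for long-term renal function;
- a rule for patients with no value;
- the covariates in the propensity score, so transplant year is not assured.

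**The concern.** A laboratory's reported eGFR is a derived figure: creatinine passed through whatever equation and reporting cap applied on that date. Transplants span eleven calendar years (2010 to 2020) and follow-up runs later. If the equation or cap changed, the same creatinine yields different eGFR values in early and late years. Should stenosis patients and controls have been measured in different years, some of that difference would be read as an effect of stenosis.

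The second issue is who has a value. A t-test or Mann–Whitney test uses whoever has a number, and the rest drop out without trace. Matching on baseline characteristics does not correct selection that arises after transplantation. If the share with a value differs between groups, and patients without one differ in kidney function, the comparison is biased. Without counts, a reader of the results could not tell.

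At stake is the secondary eGFR comparison only.

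**Working it through.** **Inputs from the document.** About 120 stenosis patients (section 4.1). Two-sided alpha 0.05, power 0.95, d = 0.5, allocation 1:1, 105 per group (section 4.4). No SD or difference is given for eGFR, so the checks below are in SD units. The shifts, imbalances and shares are assumptions.

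**1. The plan's own figure.** The noncentrality is d·√(n/2) = 0.5·√52.5 = 3.6228. With 208 degrees of freedom the critical t is 1.9714 and the exact power is 0.9501. The 105 per group reproduces and is not in dispute. Section 4.4 does not say which endpoint it serves.

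**2. Equation change.** Let s be the shift in reported eGFR caused by the change (in SD). Let q be the between-group difference in the share of values reported on the new equation. Then bias in the group difference = s × q. With 120 per group and no true effect, the noncentrality is (s·q)·√60, which gives the two-sided type I error.

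| s (SD) | q = 0 | q = 0.20 | q = 0.50 |
|---|---|---|---|
| 0.1 | bias 0; 0.050 | 0.02; 0.053 | 0.05; 0.067 |
| 0.2 | bias 0; 0.050 | 0.04; 0.061 | 0.10; 0.121 |
| 0.3 | bias 0; 0.050 | 0.06; 0.075 | 0.15; 0.212 |

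With q = 0 only noise remains. If half the values in each group are on each equation, the variance rises by the factor 1 + s²/4. At s = 0.3 that is 1.0225, so d becomes 0.5/√1.0225 = 0.4945 and power at 105 per group falls from 0.950 to 0.946. The harm therefore depends on calendar imbalance, not on the change alone.

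**3. Patients without a value.** Let r be the share with a value in a group, and let patients without a value lie g SD below those with one. The observed group mean is then too high by (1 − r)·g. With the same g in both groups, the bias in the difference is g times the difference in the unmeasured shares.
- 90% v 70% measured, g = 0.3: (0.30 − 0.10) × 0.3 = 0.06 SD.
- 90% v 70% measured, g = 0.5: 0.20 × 0.5 = 0.10 SD.
- Equal shares and equal gaps: zero.

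Swapping the groups, or letting unmeasured patients have better function, reverses the sign.

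**4. Precision.** If all 120 stenosis patients are matched 1:1, keeping 105 with a value needs 105/120 = 87.5%. Power at d = 0.5 by share measured in both groups:

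| Share measured | n per group | Power |
|---|---|---|
| 100% | 120 | 0.971 |
| 80% | 96 | 0.931 |
| 60% | 72 | 0.846 |
| 50% | 60 | 0.775 |

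**The case against.** The strongest reply is that both risks are conditional and the document shows neither condition to hold. Nothing says that the laboratory changed its equation or cap, that patients are followed elsewhere, or that stenosis patients are sampled more or less often than controls. Routine data from one centre is the declared design, and eGFR is secondary. All of this stands, and it limits the point to a minor one.

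Four stronger readings are tempting and are not supported:
- **That any equation change appears as a change in kidney function.** The planned analysis compares two groups and specifies no within-patient trend. A change shared equally by both groups cancels in the difference.
- **That the plan admits missing laboratory records.** Section 11.2 says "A substantial amount of the study population is expected to have passed away and/or has no records available about current whereabouts". That passage justifies waiving consent and concerns whereabouts. It does not separate the dead, who have no later eGFR to miss, and it says nothing about where living patients are sampled.
- **That outside values are excluded.** Section 10.2 names one source without the word only. Exclusivity is a fair inference from the absence of any other source, but it is not stated.
- **That a bias in mL/min can be quoted.** If unmeasured patients are assumed to be 8 mL/min better, with 40% of controls and 10% of stenosis patients unmeasured, the result is 3.2 − 0.8 = 2.4 mL/min in favour of stenosis. Reversing the shares gives 2.4 against. Neither the gap nor the shares come from the document.

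It can also be said that a fixed time since transplantation, with transplant year in the matching, would balance calendar time and largely remove the equation problem. That is correct, but the plan specifies neither. Differing availability of any value would remain.

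**Conclusion.** The point holds in conditional form. As written, the eGFR rule does not secure one equation, does not balance calendar time and does not account for patients without an in-house value. An equation artefact needs two things together: a change of equation or cap, and different measurement years in the two groups. A selection bias needs a different share measured between groups, together with different kidney function in those not measured (or, with equal shares, a gap that differs between groups).

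Under the assumed inputs with an imbalance, bias ranges from 0.02 to 0.15 SD for the equation and from 0.06 to 0.10 SD for selection. Both are zero under balance. The document fixes neither size nor direction, so these figures show sensitivity and are not estimates. Patient survival and death-censored graft survival do not use eGFR and are unaffected. This is a minor improvement to a secondary endpoint, worth making because it costs little before extraction and is harder to repair afterwards.

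**What to change.** In section 10.2:
1. Extract serum creatinine with sample date and in-/outpatient status, and calculate eGFR for all patients and years with one named equation.
2. Name the time points. At each, report by group the number alive with a functioning graft and the number of these with a value. State that the eGFR comparison will be interpreted with caution if the shares differ.

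In section 3 or 10, list transplant year among the propensity score covariates.

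Restriction to outpatient values, or weighting by the inverse probability of being measured, can be an optional sensitivity analysis. Neither is needed as the main analysis, and an outpatient-only rule adds a selection on health of its own.

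The cost is a changed laboratory query, one recalculation and one small table. No new tests are needed.
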